Study Title: Cerebrovascular Dysregulation in Chronic Kidney Disease

NCT # NCT05571605

Upload Date: 7/1/2025

Study Protocol:

Objective: To evaluate the effects of 12-weeks of aerobic exercise training vs stretching (control group) on dynamic cerebral autoregulation in participants with chronic kidney disease (CKD) stages III-IV.

Design: This study was a randomized controlled trial. Participants with CKD stages III-IV were enrolled for participation. All participants underwent a baseline assessment of Mean arterial pressure-Middle cerebral artery blood velocity very low frequency phase (radians) and gain (cm/s/mmHg). Participants were then randomized to a 12-week training intervention consisting of either aerobic exercise training or stretching (active control). The assessment of dynamic cerebral autoregulation was then repeated following the intervention.

Methods: Mean arterial pressure-Middle cerebral artery blood velocity very low frequency phase (radians) and gain (cm/s/mmHg) were measured during repeated bouts of sit to stand at 0.05Hz. Mean arterial pressure was measured via finger photoplethysmography. Middle cerebral artery blood velocity was measured via transcranial Doppler ultrasound. A transfer function analysis was performed to derive mean arterial pressure-middle cerebral artery blood velocity very low frequency phase (radians) and gain (cm/s/mmHg).

Location: University of North Texas in Denton, TX.

Statistical Analysis Plan:

A two-way repeated measures ANOVA (time x group) was used to compare Mean arterial pressure-Middle cerebral artery blood velocity very low frequency phase (radians) and gain (cm/s/mmHg) between time points (pre vs post) and between groups (exercise vs stretching).

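### Does analysing gain only in absolute units (cm/s/mmHg), with no normalised gain or mean velocity, undermine the comparison of exercise with stretching?

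*Combined protocol and SAP*

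**What the plan says.** The combined document is short and written in the past tense. Wherever it gives gain a unit (Design, Methods and Statistical Analysis Plan), the unit is cm/s per mmHg.

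- **Derivation (Methods):** "A transfer function analysis was performed to derive mean arterial pressure-middle cerebral artery blood velocity very low frequency phase (radians) and gain (cm/s/mmHg").
- **Velocity signal (Methods):** "Middle cerebral artery blood velocity was measured via transcranial Doppler ultrasound". Insonation angle and probe placement are not mentioned.
- **Stimulus (Methods):** phase and gain "were measured during repeated bouts of sit to stand at 0.05Hz".
- **Allocation (Design):** "Participants were then randomized to a 12-week training intervention consisting of either aerobic exercise training or stretching (active control").
- **Repeat visit (Design):** "The assessment of dynamic cerebral autoregulation was then repeated following the intervention".
- **Analysis (Statistical Analysis Plan):** "A two-way repeated measures ANOVA (time x group) was used to compare" phase and gain "between time points (pre vs post) and between groups (exercise vs stretching").

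No normalised gain (% per mmHg), mean velocity or sensitivity analysis is named.

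**The concern.** Absolute gain is the size of the velocity oscillation divided by the size of the pressure oscillation. Transcranial Doppler velocity depends on the angle between beam and vessel, and the two recordings lie on either side of a 12-week intervention. If the probe sits differently at the second visit, every velocity is multiplied by a factor c. Gain is multiplied by c too, and phase does not move. A proportional physiological change in velocity looks the same.

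One of the two analysed outcomes could thus change with no change in how strongly pressure swings are passed on relative to the prevailing velocity. Dividing gain by mean velocity cancels c, and tabulating mean velocity would show it. Neither is stated. If the worry held, a gain result, either pre versus post or between arms, could be mistaken for a change in autoregulation.

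**Working it through.** The document gives no sample size, SD, correlation, angle or measurement error, so there is no stated figure to reproduce. Every numerical input below is an assumption.

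**1. The algebra.** With H(f) = S_pv(f) / S_pp(f), replacing v by c·v gives c·H(f). Gain becomes c·gain; phase and coherence are unchanged. A transfer function on a simulated 0.05 Hz pressure-velocity pair (mean velocity 55 cm/s, gain 0.6 cm/s/mmHg, phase 0.9 rad) confirms this:

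| c | Mean velocity (cm/s) | Absolute gain (cm/s/mmHg) | Phase (rad) | Normalised gain (%/mmHg) |
|---|---|---|---|---|
| 0.8 | 44.0 | 0.482 | 0.902 | 1.096 |
| 1.0 | 55.0 | 0.603 | 0.902 | 1.096 |
| 1.2 | 66.0 | 0.723 | 0.902 | 1.096 |

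**2. Size in one participant.** An angle change from 0 to 20 degrees gives cos 20 / cos 0 − 1 = −6.0%. From 15 to 30 degrees it gives cos 30 / cos 15 − 1 = −10.3%. The same moves in reverse raise gain, and nothing in the document suggests that repositioning runs in one direction on average.

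**3. Effect on the randomised contrast.** With equal baseline gain g in expectation and no training effect, scaling contributes g·[(c_E − 1) − (c_S − 1)] to time x group, where E is exercise and S is stretching.

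- Equal scaling, 1.10 and 1.10: g·(0.10 − 0.10) = 0.
- Exercise arm only, 1.10 and 1.00: g·(0.10 − 0) = 0.10·g.
- If training truly changes gain by a fraction d, common scaling gives g·[c(1 + d) − 1] − g·(c − 1) = c·g·d. A common −6% shift would therefore shrink a true effect by 6% of itself.

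**4. Rejection rates.** There were 20,000 simulated trials per setting: 15 or 25 per arm, pre-post correlation ρ of 0.5 or 0.7, gain CV 30%, scale-error CV 8% per visit, two-sided 5%, relative transmission unchanged.

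| Scaling | Test | Rejection |
|---|---|---|
| Random error only | time x group | 4.8%–5.1% |
| Both arms −6% | time x group | 4.8%–5.0% |
| Both arms −10% | time x group | 4.6%–5.1% |
| Both arms −6% | time | 17%–37% |
| Exercise arm only −6% | time x group | 8%–12% |
| Exercise arm only −10% | time x group | 13%–28% |

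The last two rows are false positives only if the scaling is artefact that differs by arm. If training itself changes velocity proportionally, absolute gain has truly changed and a significant result is correct.

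**5. Noise.** Random scale error with coefficient of variation CVp per visit inflates the variance of the pre-post change by CVp² / [0.30²·(1 − ρ)].

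- Low end: 0.03² / (0.09 × 0.5) = 0.0009 / 0.045 = 2%.
- High end: 0.08² / (0.09 × 0.3) = 0.0064 / 0.027 = 24%.

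This adds probe error on top of the assumed 30% CV and correlation. If those already describe observed gain, the probe error is inside them and there is nothing to add.

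**6. What normalised gain would cost.** An additive shift of +5 or −5 cm/s on a mean of 50 cm/s leaves absolute gain unchanged. Normalised gain moves by 50/55 − 1 = −9% or 50/45 − 1 = +11%. For variance, let CVm be the between-visit variation in true mean velocity and k the degree to which oscillation amplitude tracks it. On the log scale, with s² = 0.09·(1 − ρ), the relative change from normalising is [s² + (1 − k)²·CVm²] / [s² + k²·CVm² + CVp²] − 1. For CVm 5% to 10% and CVp 3% to 8%:

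- k = 1: −7% to −38%.
- k = 0.5: −2% to −19%.
- k = 0: −12% to +33%. The upper end is (0.027 + 0.010) / (0.027 + 0.0009) − 1 = +33%.

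Which case applies cannot be read from the document, so neither metric is better in general.

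**The case for a change.** The strongest reply is that randomisation protects the arm contrast but not its interpretation, and not the comparison of time points, which the Statistical Analysis Plan also makes. With absolute gain alone, a reader cannot tell rescaled velocity from altered relative transmission. The remedy is cheap: one division per recording and one table, presumably from a signal already recorded.

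Part of this stands. The pre-post comparison is exposed if the average shift is not zero, hence the 17% to 37% above. But the Objective is exercise versus stretching, a between-arm question that the time effect does not answer, and no reason for a non-zero average shift is given. A table of mean velocity by arm and visit would help a reader.

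The rest goes less far than it seems. Normalised gain cancels proportional scaling from any cause, so it cannot tell a moved probe from a proportional physiological change. Where absolute and normalised gain disagreed, nothing would say which to believe. And in so brief a retrospective summary, what is not stated may still have been recorded or tabulated.

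**Conclusion.** The concern does not hold. Its algebra is exact and the document names no companion measure, but the plan uses one legitimate definition of gain throughout, and the time x group comparison of that outcome is sound as written. Scaling unrelated to arm leaves the interaction error rate at 4.6% to 5.1% and costs at most some precision (2% to 24% more variance in the pre-post change). Phase, the other outcome, is untouched by proportional scaling.

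This rests on scaling artefact being unrelated to arm; the document gives no evidence either way. It also rests on the assumed CVs, correlations and 15 to 25 participants per arm. If measurement conditions were shown to differ between arms, the question would reopen, with interaction rejection of 8% to 28% under the shifts examined. As matters stand, normalised gain and mean velocity are welcome supportive reporting. Leaving them out is neither an error nor clearly inferior practice.

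### The time × group ANOVA is valid, but it fixes the baseline slope at 1 and does not name the treatment-effect term; naming the interaction and adding an ANCOVA is cheap and usually more precise

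*Combined protocol and SAP*

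**What the plan says.** The Objective is a comparison of arms: "To evaluate the effects of 12-weeks of aerobic exercise training vs stretching (control group) on dynamic cerebral autoregulation". Under Design, "This study was a randomized controlled trial". The baseline came first ("All participants underwent a baseline assessment of Mean arterial pressure-Middle cerebral artery blood velocity"), participants were randomised after it, and "The assessment of dynamic cerebral autoregulation was then repeated following the intervention". Each participant therefore has one value before randomisation and one after the intervention for each of two outcomes, phase and gain.

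The Statistical Analysis Plan is a single sentence. "A two-way repeated measures ANOVA (time x group) was used to compare" the two outcomes "between time points (pre vs post) and between groups (exercise vs stretching". It mentions no baseline covariate, does not say which model term is the treatment effect, and specifies no effect estimate or confidence interval. The document gives no sample size, SD, pre-post correlation, effect size or significance level. It is written in the past tense and carries an upload date of 7/1/2025.

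**The concern.** There are two linked points.

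**Precision.** The ANOVA interaction subtracts the whole of each participant's baseline. This is optimal only if a one-unit difference at baseline predicts a one-unit difference afterwards. If the true slope is below 1, subtraction over-corrects, and the estimate moves with chance baseline differences between the arms. That is where the precision is lost; it is not a separate bias. An ANCOVA on the same data estimates the slope, so a usually more precise answer to the Objective is available from measurements already taken.

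**Which term.** A two-way model has a time effect, a group effect and their interaction. Only the interaction estimates the full treatment effect. The comparisons that the plan spells out correspond to the two main effects. The group main effect averages a pre-randomisation value with the post value, and the time main effect does not compare the arms. A reader cannot tell from the text which result answers the Objective.

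**Working it through.** **Inputs from the document:** two randomised arms, baseline before randomisation, one post value, and a time × group ANOVA as the only analysis. There is no stated sample size or power to reproduce.

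**Assumptions:** normal data, equal arms, no dropout. Let s be the pre SD, k the post SD divided by the pre SD, ρ the pre-post correlation, n the number per arm and δ the true effect. Because ρ, k and n are not given, ranges are shown.

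**1. The interaction is a change-score t-test.** With two groups and two time points this is an identity. In a test data set the interaction F was 8.3253 and the squared t on change scores was 8.3253, with the same estimate (1.0149).

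**2. Dependence on baseline imbalance.** Given a baseline difference D between arms, the interaction estimate has expectation δ − (1 − ρk)D. Simulation at 20 per arm agrees: slope −0.603 at ρ = 0.5, k = 0.8 (formula −0.60), and −0.003 at ρ = 0.8, k = 1.25 (formula 0).

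**3. Variances.**
- Interaction: s²(1 + k² − 2ρk)(2/n)
- ANCOVA, slope estimated: s²k²(1 − ρ²)(2/n)(1 + 1/(2n − 4))
- Large-sample difference: s²(1 − ρk)²(2/n), which is zero when ρk = 1

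For k = 1 the ratio of ANCOVA to interaction variance is (1 + ρ)/2 × (1 + 1/(2n − 4)). For example, at n = 20 and ρ = 0.5 it is 0.75 × (1 + 1/36) = 0.771.

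| k | n per arm | ρ = 0.3 | ρ = 0.5 | ρ = 0.7 | ρ = 0.9 |
|---|---|---|---|---|---|
| 1 | 20 | 0.668 | 0.771 | 0.874 | 0.976 |
| 1 | 10 | 0.691 | 0.797 | 0.903 | 1.009 |
| 1 | 6 | 0.731 | 0.844 | 0.956 | 1.069 |
| 1 | 5 | 0.758 | 0.875 | 0.992 | 1.108 |
| 0.8 | 20 | 0.516 | 0.587 | 0.645 | 0.625 |
| 0.8 | 6 | 0.565 | 0.643 | 0.706 | 0.684 |
| 1.25 | 20 | 0.806 | 0.918 | 1.008 | 0.976 |
| 1.25 | 6 | 0.883 | 1.004 | 1.103 | 1.069 |

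Values below 1 favour the ANCOVA. Simulation with 60,000 trials per setting (k = 1) gave 0.733/0.845/0.961/1.069 at n = 6 and 0.756/0.880/0.997/1.108 at n = 5.

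**4. Break-even for k = 1.** Setting the ratio to 1 gives ρ = (2n − 5)/(2n − 3): 35/37 = 0.946 at n = 20, 15/17 = 0.882 at n = 10, 7/9 = 0.778 at n = 6 and 5/7 = 0.714 at n = 5. Above these values the ANCOVA loses a little.

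**5. Confidence intervals and power, k = 1.** The mean 95% CI width of the ANCOVA relative to the interaction, at ρ = 0.3/0.5/0.7/0.9, is 0.82/0.88/0.93/0.99 at 20 per arm and 0.86/0.93/0.99/1.04 at 6 per arm. Power for an illustrative effect of 0.8 pre-SD, two-sided 5%:

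| n per arm | Analysis | ρ = 0.3 | ρ = 0.5 | ρ = 0.7 | ρ = 0.9 |
|---|---|---|---|---|---|
| 20 | Interaction | 55% | 69% | 89% | >99% |
| 20 | ANCOVA | 72% | 80% | 93% | >99% |
| 6 | Interaction | 19% | 24% | 37% | 80% |
| 6 | ANCOVA | 24% | 28% | 38% | 76% |

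**6. Validity.** Simulated type I error of both methods (n = 5, 6, 10 and 20; ρ = 0.3 and 0.9; k = 1) lay between 0.048 and 0.051.

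**7. The group main effect.** The two arms have equal expectation before treatment and differ by δ afterwards, so the mean of pre and post differs by (0 + δ)/2 = δ/2. In simulation at 20 per arm a true effect of 0.80 gave 0.40, with power of 0.34, 0.30 and 0.27 at ρ = 0.3, 0.5 and 0.7.

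**The case against.** The best defence is that nothing here is an error. The interaction uses the baseline, is unbiased under randomisation and holds its type I error. Choosing ANCOVA over change scores is a matter of efficiency. The inputs that would show a benefit in this trial are all absent, and the range includes losses: with k = 1.25 and 6 per arm, the ANCOVA gains only at the lowest correlation shown. The past tense suggests that the analysis has been done, in which case an ANCOVA can only support the main result. Finally, time × group is the usual notation for a model with its interaction, and the listed comparisons may simply define the two factors.

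Most of this stands. The ANOVA should not be called wrong, the size of the gain here cannot be claimed, and nothing shows that a main effect was reported as the result. Two things remain. The large-sample variance of the ANCOVA is never higher than that of the interaction, and in small samples the possible loss is modest beside the possible gain. And although the notation suggests the interaction, the sentence does not say that it is the treatment effect and asks for no estimate of it.

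**Conclusion.** The concern holds as a point of efficiency and clarity; it does not threaten the validity of the trial. The interaction is a sound analysis with the baseline slope fixed at 1. An ANCOVA would usually be more precise. Across the settings tabulated, the change in variance runs from a 48% reduction (k = 0.8, ρ = 0.3, 20 per arm) to an 11% increase (k = 1, ρ = 0.9, 5 per arm). Those figures assume normal data, equal arms and no dropout, and where this trial lies in the range is unknown. The need to name the interaction and report its estimate does not depend on ρ, k or n.

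**What to change.** If outcome data by group have already been examined, whether or not the ANOVA was pre-specified, state:

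> For phase and for gain separately, the time × group interaction is the ANOVA term that estimates the treatment effect. It is the reported main analysis, given as exercise minus stretching in change with a 95% CI. As an additional post hoc analysis, exercise minus stretching in the post-intervention value is reported from an ANCOVA on randomised group and the participant's own baseline value, with a 95% CI, whatever its result.

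Make the ANCOVA primary, with the interaction as supporting analysis, only if no outcome data by group have been examined. This ordering prevents the analysis from being chosen by its result.

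The cost is a few sentences in the SAP or report and one extra regression per outcome, with no new data. The covariate takes one degree of freedom. Expect little gain or a small loss if the correlation is high in a very small sample, or if ρk is near 1.
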